4.5.2 Digital Data Platform and Wearables Pilot

Patients who enrol onto the pilot trial, either as a follow on from the patient focus groups or through recruitment via the Sickle Cell Society, London North West University Healthcare NHS Trust, or Barts Health NHS Trust, will be able to use either their own existing device or will be provided with a comparable market available smartwatch by the study. Data points, as summarised in Section 4.3, will be collected in an automated fashion on an ongoing basis, before transmission to a secure cloud database. This provides a novel approach to the monitoring of SCD that forgoes the need for patients to manually record information themselves and provides the potential for a larger patient cohort through remote monitoring, collecting a greater wealth of more in-depth, real-time and longitudinal data from patients during their daily lives. This supports a higher degree of compliance through decreased intrusion and an improved quality of data through improved objectivity and the elimination of retrospective recall. Furthermore, the utilisation of a wearable device provides the establishing of a baseline identified by 24/7 monitoring of data collection, providing a precise comparison for any patterns and changes over time to inform improved treatment pathways.

Patients will be set up with an electronic account and access to the digital platform through which their personal data can be accessed and visualised, and any additional metrics – such as body weight, dietary intake, emotional wellbeing, and additional medication consumption – can be manually input by the patient themselves as desired.

5. Project Plan

As part of the process of engaging patients prior to the full study and technology pilot trial, the project entails a series of initial pre-study patient focus groups over a 2-month period, in order to gather the relevant insights to ensure the study design, steps and outcomes are curated around a patient-centric outlook. Our intended timetable is as follows:

Project Stage	2 months	3 months	12 months				1 month
1 Pre-Study Focus Groups Engaging patients in study development prior to initiation of the full wearable pilot							
2 Pilot Study Enrolment Patients recruited to participate in the pilot through pre-study focus groups, the Sickle Cell Society & participating trusts							
3 Wearables Pilot Study Trialling of the live wearable and digital platform with patients, data collection, and analysis							
4 Post-Study Focus Groups Sessions with participating patients to gather feedback from the pilot and outline next steps accordingly							

6. Population

Any patient with a diagnosis of SCD, or child under 16 years of age with parental guidance, will be eligible to participate in the digital data platform / wearable pilot and focus group studies.

Patients will be recruited through multiple channels in order to ensure the involvement of as large and heterogeneous a patient cohort as possible. For these initial focus groups and digital data platform / wearable pilot trial, this recruitment will therefore be through the Sickle Cell Society's patient network, as well as patients treated at the hospitals of London North West University Healthcare NHS Trust and Barts Health NHS Trust. Estimates from the National Haemoglobinopathy Registry suggest a potential patient cohort of 1,324 patients at Barts Health NHS Trust, and an additional 418 patients at London North West University Healthcare NHS Trust. It is hoped that a greater number of patients outside of the London region will also be included via the Sickle Cell Society, and that the trial will be expanded to include additional treatment centres with time.

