3.2 Secondary Aim

A secondary aim is to further develop the features and usability of the data platform and wearable device through a patient lens, in an ancillary study with patient focus groups around 3 key research areas: SCD's impact on psychological wellbeing, the usefulness of wearables in day-to-day patient life, and concerns around consenting to data sharing.

4. Project Design

[figure not shown]
The project will be a combination of focus groups and data collection. This will be an ongoing, data-driven project, revolving around the collation of episodic and live data points including admission, diagnostic, pathology, radiology, primary care, pharmacy, physiotherapy, Hospital Episode Statistics (HES), Open Data, clinical data points, and the incorporation of live wearable device data. Cultivation of the most relevant data points in the context of SCD has been ongoing with the support of expert clinicians in the field, and will be further developed through the input of patients themselves during a series of patient focus groups, in order to establish what the most important factors are to SCD care through a patient-lens. Wearable devices will be provided to patients who do not already own one, in support of the unified digital data platform, within a pilot study with consenting patients who choose to register following these patient focus groups, as well as those who have enrolled through the Sickle Cell Society and from patient cohorts at treatment centres such as London North West University Healthcare NHS Trust and Barts Health NHS Trust. The project's development will further be supported through the inclusion of a number of focus groups between specialist doctors and nurses, as well as healthcare managers, public health officials and commissioners.

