4.1 Sample Size

There is an estimated 12,500-15,000 people living with SCD in the UK^{xvii}. Our patient sample size is based upon an estimated minimum proportion of the total population of patients with SCD we aim to enrol onto the digital platform and wearables pilot study, assuming not all patients will be reached by the initial programme launch through the Sickle Cell Society and partnering trusts, and that of those who are, not all will provide consent or be interested in participating. As such, our starting goal is to recruit 2% of the total UK SCD patient population, at 300 patients.

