4.2 Data Sources, Access and Flow

From the starting point of sources including hospital Electronic Medical Records (EMRs), open data, and Hospital Episode Statistics (HES), the data platform will integrate written medical and primary care records from GPs, structured and unstructured EMIS/TPP records, as well as genetic information through external organisations such as 23andMe, following full patient consent. With additional wearables collected data (Section 4.3), these sources will be combined within a specialised SCD unified data platform to allow the application of a set of advanced algorithms, providing granular analysis of key patient metrics.

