7.2 Patient Withdrawal

Patients may voluntarily withdraw from the study at any time, as protected by GDPR, or be dropped from it at the discretion of the responsible clinician (investigator) at the NHS Trust. Patients may be withdrawn from the study if any of the following occur:

Patient or parent withdrew consent

Lost to follow-up

Death

Administrative problems

For patients who are lost to follow-up, the investigator will show 'due diligence' by documenting steps taken to contact the patient, such as dates of telephone calls, and mailings.

8. Statistical Analyses

An initial high-level investigation using descriptive analysis will be conducted across all variables in order to identify key trends and insights, from which further correlations and statistical significance will be tested. This will predominantly be performed using IBM SPSS Statistics 24 and Microsoft Excel, collected data analysed for outliers through Boxplot and Q-Q Plots, for normal distribution using Shapiro-Wilks testing, and for homogeneity of variance using Levene's testing. Due to the exploratory nature of the study, hierarchical stepwise regression of the outlined data points (Section 4.2 & 4.3) will be conducted, and any outliers detected through assumption testing will not be immediately excluded from analyses, instead further investigated to identify any clinically significant causes. For data that do not violate these assumptions, either independent t-tests (for experiments with two experimental groups) or one-way ANOVA (for experimental groups of 3 or more) will be performed, with Bonferroni post-hoc testing. Those that do violate these assumptions will undergo non-parametric Kruskal-Wallis testing. Each analysis will be based upon demographic variables, such as age and gender, correlated against genetic and clinical variables including hospital admissions, comorbidities, genotype, phenotype, and wearables collected data (Section 4.3). Those with p-values below 0.05 will be considered as statistically significant and undergo further study.

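### Patients wear their own or a supplied watch, but device identity is not logged or named in the analysis, so between-patient comparisons could show device differences as clinical ones

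*Protocol*

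**What the plan says.** Section 4 (Project Design) states: "Wearable devices will be provided to patients who do not already own one". Section 4.5.2 repeats the rule for the pilot: a patient uses "either their own existing device or will be provided with a comparable market available smartwatch by the study". Prior ownership therefore decides the device. Neither section sets a minimum list of metrics that an owned device must record, and neither asks for the device to be identified in the data.

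Section 4.2 says of the hospital, GP, genetic and wearable data that "these sources will be combined within a specialised SCD unified data platform". Section 4.3 lists the wearable and app metrics, among them heart rate, oxygen saturation, temperature, blood pressure and ECG. Device make or model is in neither section.

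Section 8 plans that "hierarchical stepwise regression of the outlined data points (Section 4.2 & 4.3) will be conducted", together with t-tests, one-way ANOVA or Kruskal-Wallis tests. Demographic variables are to be "correlated against genetic and clinical variables including hospital admissions, comorbidities, genotype, phenotype, and wearables collected data". On the threshold it says: "Those with p-values below 0.05 will be considered as statistically significant and undergo further study".

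Section 4.5.2 also says that continuous monitoring gives a baseline against which later patterns and changes are compared.

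**The concern.** The device is not assigned by the study; it follows from what the patient already owned. Eligibility starts at age 5 and has no upper limit (Section 6.1), and Section 6 seeks a cohort as varied as possible, so ownership could well differ by age or by other characteristics that Section 8 relates to wearable readings. Owned watches may also be of several models with different sensors, and Section 2.4 itself notes that several device types exist and that sensor capability is changing quickly.

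If one kind of device reads higher than another, two groups with different ownership will differ in mean reading even when the patients do not differ. If some owned models lack a metric, the analysis of that metric is limited to a subset defined by device choice. The primary aim (Section 3.1) is to relate vital parameters to illness and healthcare use, and Section 8 passes the associations found to predictive algorithms, so an artefact could be carried forward.

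**Working it through.** **The plan's own figure.** Section 4.1 says "our starting goal is to recruit 2% of the total UK SCD patient population, at 300 patients", from an estimated 12,500 to 15,000 people. 0.02 x 15,000 = 300, which matches. 0.02 x 12,500 = 250, so 300 is 2% of the upper end of the range. The protocol gives no SD, device offset, ownership share or group size. Everything below except the total of 300 is therefore assumed.

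**Assumed inputs.** Two groups of 150 with no true difference; SD 3 points (for example of oxygen saturation); a constant offset of 1 or 2 points between owned and supplied devices; own-device share differing between groups by 0, 20 or 40 percentage points; two-sided 5% test (Section 8 does not state sidedness).

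**Formulas.**
- Spurious difference B = offset x ownership gap.
- SE = 3 x sqrt(2/150) = 0.346.
- False-positive rate = Phi(B/SE - 1.96) + Phi(-B/SE - 1.96).

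| Ownership gap | Offset | B | B/SE | False-positive rate |
|---|---|---|---|---|
| 0 | 1 or 2 | 0 | 0 | 5.0% |
| 20 points | 1 | 0.2 | 0.58 | 8.9% |
| 20 points | 2 | 0.4 | 1.15 | 21.1% |
| 40 points | 1 | 0.4 | 1.15 | 21.1% |
| 40 points | 2 | 0.8 | 2.31 | 63.7% |

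**Refinement.** If 3 is the SD among patients on the same kind of device, mixing devices adds variance. At 70% v 30% ownership and a 2-point offset, the variance is 9 + 4 x 0.21 = 9.84, the SD 3.137 and the SE 0.362. B/SE is then 2.21 and the rate 59.8%. Hence about 60 to 64% for the extreme case.

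**Does a device term help?** In simulations of 4,000 trials per scenario, with offsets in SD units, the rate without a device term was 13.5% (60% v 40% ownership, 0.5 SD) and 38.7% (70% v 30%, 0.5 SD). With a two-level device term it was 5.4% and 4.6%. For within-patient change on one unchanged device, with no term, it was 4.7% and 5.5%. A constant offset cancels in the change, so the exposure lies in between-patient comparisons of levels.

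**The case against.** The strongest objection is that this rests on silence about a covariate. The variable lists in Section 8 are open-ended ("Each analysis will be based upon demographic variables, such as age and gender, correlated against genetic and clinical variables", followed by examples), nothing in them excludes device, and adjustment covariates are commonly left to an SAP, which is not at hand. Nor does combining sources in Section 4.2 say that readings from different watches are treated as interchangeable; it describes joining record systems. A reader might infer that the protocol prescribes unadjusted pooling of devices. It does not say that.

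A reader might also infer that confounding is established. It is not: no section reports that ownership varies with patient characteristics or that devices read differently. The protocol intends the supplied watch to be comparable, and Section 2.4 says that current watches can measure blood pressure, oxygen saturation and ECG, so gaps in owned devices are a possibility only. The study is exploratory, and a p-value below 0.05 leads to further study.

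These points remove the claim of demonstrated bias. Two things remain. The mixed-device design is fixed in the protocol, and an SAP can fit a device term only if device identity was captured while the data were collected. The protocol does not require that. Section 7 does ask which watch a patient owns, but only of focus group participants, and Section 4.5.1 describes those answers as anonymised. Calling the supplied watch comparable also does not make the various owned models comparable with one another.

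**Conclusion.** The point holds as a conditional one. Ownership decides the device, device identity is not among the data listed for collection, and Section 8 compares wearable values between patients without naming device. Where ownership differs between the compared groups and devices differ by a systematic offset, a difference in levels can be a device difference.

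The size is unknown. The figures of 5% (no gap), about 9 to 21% (20-point gap) and about 60 to 64% (40-point gap with a 2-point offset) rest wholly on assumed inputs, and the last pairs the largest gap with the largest offset. They show how the error behaves and do not predict it for this study. It would be wrong to read the whole study as exposed: change from the Section 4.5.2 baseline on one unchanged device is largely protected against a constant offset. That protection is lost if a patient changes device and the change is not recorded. The study remains viable, and this is an improvement worth making before enrolment.

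**What to change.** - In Section 4.3 or 4.5.2, require make, model and firmware to be logged for each data stream, with the date of any change of device. This has to be done prospectively, since it may not be recoverable later.
- Where the question allows, analyse deviation from the patient's own baseline on the same device.
- For between-patient comparisons of wearable levels, use regression or ANCOVA with a grouped device factor, such as supplied v own, or the main device families with sparse models combined. A separate level for every model would be too sparse in 300 patients.
- Repeat those comparisons in supplied-watch users only, as a sensitivity analysis.
- Report for each Section 4.3 metric how many patients' devices record it.

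The cost is small: one logged field, a few degrees of freedom, and regression in place of simple t-tests or Kruskal-Wallis tests for these comparisons. The supplied-watch analysis will be smaller and less precise, and serves only as a check.

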4.3 Wearable & App Data Points

Following specification of the most crucial metrics, live data points will be integrated into the unified data platform directly from patients through the use of wearables and ongoing monitoring of factors, or through optional manual input of additional information, such as a pain scale of mood, through the platform's mobile app by patients. These include:

Metric	Rationale
Heart Rate	A fast heart rate is linked to anaemia and low blood O ₂ , stress, and panic attacks.
Blood O₂ Saturation	Low arterial blood oxygen saturation is common in SCD, and Obstructive Sleep Apnoea is also highly prevalent in patients with SCD.
Body Temperature	Raised or decreased temperatures are linked to crises, with low body temperatures known to trigger vasoconstriction. High temperatures can also be an indication of infection and in turn trigger crises.
Blood Pressure	Blood pressure is known to be lower in SC anaemia, with relative hypertension linked to an increased risk of stroke, pulmonary hypertension, renal dysfunction & death. This can also be used as an important indicator of stress.
ECG Abnormalities	ECG abnormalities are common in SCD & early identification / intervention can help to prevent serious cardiac events, e.g. Myocardial Infarction during VOC.
Sleep Cycles	Disrupted sleep cycles / patterns are linked to increased pain and periods of crisis.
Fitness & Activity	Low activity levels may be an indicator of the onset of a crisis, and certain exercises are linked to relieving pain.
Nutrition / Diet / Medications taken	Can be an important indicator of emotional wellbeing & pain levels, with disrupted eating patterns or loss of appetite potentially indicating periods of chronic pain or VOC.
Pain and Symptoms	Provides a direct monitor of patient wellbeing and will support correlation of metrics with symptoms of SCD pathologies.

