An additional focus for the study regards data collected over extended periods of time and the progression of the disease state over this period, therefore requiring the inclusion of two independent variables. For such data, this will require Mauchly's test for sphericity in addition to Shapiro-Wilks testing for normal distribution. These data will then be tested for statistical significance using a two-way repeated measures ANOVA with a Bonferroni adjustment. Each step of the analytical output will be reported alongside changes in variance and F change, and collinearity of the independent variables will be investigated within the regression model.

This statistical analysis will in part feed into and be supported by the data platform's advanced AI and ML algorithms. However, the primary purpose of the AI technology will revolve around the predictive element of this study, highlighting potential outcomes and suggestions for optimal treatment pathways based upon the statistical analysis conducted, and key trends or associations identified.

9. Administrative Procedures

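### Over a single 12-month pilot with 3-month enrolment and no concurrent group, season and time on study are largely confounded, so seasonal change can be mistaken for disease progression

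*Protocol*

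**What the plan says.** The Section 5 timetable has columns of 2, 3, 12 and 1 months against four stages. The text states that "the project entails a series of initial pre-study patient focus groups over a 2-month period", which ties the first column to the first stage. The 3-month column then belongs to enrolment ("Patients recruited to participate in the pilot through pre-study focus groups, the Sickle Cell Society & participating trusts") and the 12-month column to the pilot itself ("Trialling of the live wearable and digital platform with patients, data collection, and analysis").

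Section 4.5.2 takes as the reference for change "the establishing of a baseline identified by 24/7 monitoring of data collection", and describes it as "providing a precise comparison for any patterns and changes over time to inform improved treatment pathways". No concurrent comparison group is described.

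Section 8 sets out a further analysis of "data collected over extended periods of time and the progression of the disease state over this period". These data are to be "tested for statistical significance using a two-way repeated measures ANOVA with a Bonferroni adjustment". The two factors, the time periods and the baseline window are not named. Neither season nor calendar time is mentioned anywhere in the protocol.

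**The concern.** If all patients start within about three months of each other and are followed once round the calendar, study month and calendar month are nearly the same variable. Any measure with a yearly cycle then changes over study time even when the disease does not. Activity, sleep and hospital use are plausible candidates. Each patient's baseline is taken in one season and later months are compared with it, so the patient's own baseline does not remove the cycle.

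The primary aim in Section 3.1 relates long-run patterns in vital parameters to illness and healthcare use, and Section 8 feeds the statistical results into predictions and suggested treatment pathways. A seasonal pattern labelled as progression would be carried into both.

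**Working it through.** The protocol gives no figure for season, so there is none to reproduce. Its sample size enters the last step: 0.02 × 15,000 = 300 (Section 4.1).

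**Inputs from the protocol:** 3-month enrolment, 12-month pilot, N = 300, significance at p < 0.05.

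**Assumptions:** a sinusoidal yearly cycle of amplitude A, start dates uniform over the 3 months, no true progression.

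**1. Share of the cycle left after staggered starts.** With starts uniform over W months, averages by study time keep sin(πW/12)/(πW/12) of the cycle.
- W = 0 (common start): 100%
- W = 3: sin(π/4)/(π/4) = 0.7071/0.7854 = 0.90
- W = 6: 64%
- W = 12: 0%

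At W = 3, study time accounts for 0.90² = 0.81 of the seasonal variance.

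**2. Differences between study quarters.** Averaging within a 3-month quarter multiplies by a further 0.90, so the amplitude of the quarter means is 0.90 × 0.90 = 0.81A. Quarters 1 and 3 are half a cycle apart and differ by at most 2 × 0.81A = 1.62A. The range across the four quarters is smallest when the calendar phase falls midway: 1.62A × cos 45° = 1.15A. So whatever the start date, the quarter means spread by 1.15A to 1.62A.

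**3. Where the bias lies in the year.** Averaging within a month multiplies by sin(π/12)/(π/12) = 0.989. Two months that are k months apart differ by at most 2 sin(πk/12) × 0.989 × 0.90 × A.
- Month 7 v month 1 (k = 6): 2 × 1 × 0.989 × 0.90 = 1.78A
- Month 12 v month 1 (k = 11): 2 × 0.2588 × 0.989 × 0.90 = 0.46A
- Month 13 v month 1 (k = 12): 0, but this lies outside a 12-month pilot

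**4. Effect on the test.** Simulation with no progression, N = 300, four quarters, assumed intraclass correlation 0.5, random calendar phase and 3,000 runs per case. For simplicity it used a one-factor repeated measures ANOVA on time. Share of runs with p < 0.05, starts spread over 3 months:

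| A (in SD, assumed) | Time effect, four quarters | Quarter 4 v quarter 1 |
|---|---|---|
| 0 | 5% | 5% |
| 0.05 | 19% | 11% |
| 0.1 | 65% | 26% |
| 0.2 | over 99% | 65% |

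With starts spread over 12 months the time test stayed near 5% at every A.

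**5. Can calendar terms separate the two?** Adding sine and cosine of calendar time to a model with a linear time slope multiplies the variance of that slope by 2.0 with 3-month enrolment and 12 months of follow-up (2.7 with a common start). With 24 months the factor would be 1.1 to 1.2.

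**The case against.** The strongest reply is that this is an omission and that the statistical analysis plan, not shown here, may deal with it. Section 8 does not name the ANOVA factors, so calendar terms are not excluded. Section 8 also speaks of extended periods without limiting them to the pilot year. The platform holds historical records (Sections 3.1 and 4.2), the study is called ongoing (Section 2.4), and further centres are hoped for (Section 6). The phrase about a precise comparison can be read as rationale for the device and not as an analysis rule.

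Part of this stands. Historical records can show past seasons for hospital use, and calendar terms would help. But no earlier wearable series is described, and neither longer follow-up nor later centres appear in the timetable. The test and its target are stated, and that test as written has nothing to separate season from progression.

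Some stronger readings are tempting but not supported:
- **That everyone starts together after the window.** The bars of the timetable are not legible in the text, and starting on enrolment is not ruled out. This matters little: it moves the retained share from 100% to 90%.
- **That season will be read as progression.** The documents give no seasonal amplitude. The temperature row of Section 4.3 ("Raised or decreased temperatures are linked to crises, with low body temperatures known to trigger vasoconstriction") is the rationale for measuring body temperature. It is not evidence about weather.
- **That a cohort started in summer drifts down over the year and one started in winter drifts up.** If entry is centred on the seasonal peak or trough, a straight line over the full year has zero seasonal slope, because the measure moves away and comes back. The largest fitted drift, 6/π × 0.90 = 1.72A, needs entry centred about three months from the peak, and a straight line is not the planned test.
- **That month 12 against month 1 is season-matched.** The months are eleven months apart, and used alone the contrast drops ten of the twelve months.

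**Conclusion.** The point holds as confounding in the design, not as a demonstrated bias of known size. On the stated timetable about 90% of any yearly cycle stays in averages by study time, so the within-pilot time effect cannot by itself distinguish season from progression, and the on-study baseline is not on its own a precise comparison.

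In units of the unknown A, the apparent change with no progression is 1.15A to 1.62A across quarters and up to 1.78A at mid-year, falling to at most 0.46A by month 12. If A were 10% of the mean (an assumption), the largest quarter difference would be about 16%. These figures rest on a sinusoidal cycle, on uniform starts, on reading the 3 and 12 months from column headings, and on 12 full months of data per patient. The last is not stated, since analysis shares the same 12-month stage. The simulated error rates also depend on the assumed correlation and on a simplified one-factor test.

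**What to change.** In Section 8:

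1. State that the within-pilot time effect will be reported as season plus progression and not interpreted as progression. Qualify the wording on the baseline in Section 4.5.2 to match.
2. For healthcare utilisation, compare each pilot month with the same calendar month in that patient's earlier linked records.
3. For wearable measures, keep all months and add sine and cosine terms in calendar time to the longitudinal model, with time on study as a simple trend. Report month 12 against month 1 as a sensitivity analysis, described as near-matched, with a residual of up to 0.46A.

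**Cost.** These are changes of wording and analysis on data the plan already intends to collect. The calendar terms roughly double the variance of a linear time slope and cannot separate an arbitrary month-by-month pattern from season. The historical comparison serves only utilisation, and only patients whose records are linked. An exact seasonal match for wearable measures would need data from month 13 onward, which the timetable does not provide.
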